This material is the property of the NYU School of Medicine and Langone Medical Center. Do not disclose or use except as authorized in writing by the study sponsor
Interventional Template Version: 11 January 2019

PANAS	Positive and Negative Affect Schedule
PDDS	Patient Determined Disability Scale
PI	Principal Investigator
QA	Quality Assurance
QC	Quality Control
RAVLT	Rey Auditory Visual Learning Test
RRMS	Relapse Remitting Multiple Sclerosis
SAE	Serious Adverse Event/Serious Adverse Experience
SDMT	Symbol Digit Modalities Test
SOP	Standard Operating Procedure
STAI	State-Trait Anxiety Inventory
tDCS	Transcranial Direct Current Stimulation
TLFB	Timeline Followback Method Assessment
US	United States
TMS	Transcranial magnetic stimulation

CONFIDENTIAL

This material is the property of the NYU School of Medicine and Langone Medical Center. Do not disclose or use except as authorized in writing by the study sponsor
Interventional Template Version: 11 January 2019

Protocol Summary

Title	A Telehealth tDCS Approach to Decrease Cannabis Use: Towards Reducing Multiple Sclerosis Disability
Short Title	A Telehealth tDCS Approach to Decrease Cannabis Use in MS
Brief Summary	We will recruit 52 patients with MS, CUD, and elevated distress (K10 score 10-35) in a double-blinded, parallel-arm, sham-controlled trial of a completely at-home intervention. We will test 20x20-minute RS-tDCS (2.0 mA, DLPFC: left anodal) paired with guided mindfulness meditation to decrease distress and cannabis use. Participants will be randomized 2:1 to active vs. sham tDCS.
Phase	Phase 2
Objectives	
- Evaluate the effect of DLPFC tDCS to decrease distress component of cannabis use disorder- Evaluate the effect of DLPFC tDCS to reduce cannabis use- Evaluate if DLPFC tDCS related change in cannabis use is linked to a change in distress
Methodology	2:1 Randomized, Parallel-Arm, Double-Blind, Sham-Controlled Design
Endpoint	
Primary Endpoints:
 
- Decrease in Distress by treatment End- Decrease in Cannabis Use by treatment End 
Secondary Endpoints:
 
-Decrease in Distress through 3-month follow-up-Decrease in Cannabis Use through 3-month follow-up
Study Duration	2 years
Participant Duration	Approximately 4.5 months (4-6 weeks of intervention + follow-ups at 1, 2, and 3 months)
Duration of IP administration	20x20 minutes daily sessions of DLPFC tDCS combined with mindfulness meditation

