2.3 Rationale

The application of tDCS to substance use disorder is not novel on its own⁷⁰. However, no study to date has evaluated tDCS for the treatment of CUD¹⁰⁴, and all studies of tDCS in other substance use disorders have required onsite delivery of treatment, resulting in mixed findings following “underdosed” treatment periods in terms of number of applications (i.e., <5) and duration of treatment period (i.e., 1 week or less)¹⁰⁵. Further limiting comparison/conclusion across studies to date has been the broad variation in other parameters such as electrode montage, stimulation intensity, duration, frequency, and concurrent activity during the stimulation^{70,104}. tDCS represents a promising treatment to reduce the distress component of the addiction cycle, and must be evaluated in a dosage that is likely to be effective.

Hypothesis: When given in a multisession paradigm, active vs. sham tDCS delivered to the DLPFC will reduce distress and cannabis use in patients with MS.

[figure not shown]

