4.2 Study Endpoints

4.2.1 Primary Study Endpoints

- Change in distress measured by Kessler Psychological Distress Scale (K10) and Positive and Negative Affect Schedule (PANAS) between baseline and treatment-end.
- Change in cannabis use measured by Timeline Followback Method Assessment (TLFB), Marijuana Craving Questionnaire (MCQ-17), Daily Sessions, Frequency, Age of Onset, and Quantity of Cannabis-Use Inventory (DFAQ-CU) and Cannabis Withdrawal Scale (CWS) between baseline and treatment-end.

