10.2 Statistical Hypotheses

We will test the hypotheses that there is an interaction between treatment (active vs. sham) and time on 1) distress (K10 & PANAS-NA) and 2) use (TLFB), with additional outcomes addressing mood/anxiety (BDI, STAI), detailed cannabis use (DFAQ-CU), craving (MCQ-17) and withdrawal (CWS).

If the interaction effect for an outcome is significant, we will conclude there is statistical evidence of overall treatment effect. If the spaghetti plots suggest trends (e.g., linear, quadratic, or piecewise changes) we will treat time as a continuous variable and fit repeated measures regression models along with group and its interaction with continuous time as independent variables.

In supplementary analyses, additional factors or covariates will be included in the models (along with their corresponding interactions with group and time) to examine the potential influence of gender, age, MS disability (PDDS), depressive symptoms (BDI), anxiety (STAI) and CUD severity (CUDIT-R) on responsiveness to active vs. sham treatment.

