10.4.2 Analysis of the Primary and Secondary Endpoint(s)

The efficacy of RS-tDCS to effect the outcomes of each Aim 1 & 2 will be tested using linear mixed effects models. The dependent measures (K10 score, NA, percent of days of use, CWS, MCQ-17) will be nested within timepoint (Visit 1, 5, 10, 15, 20), with active/sham as fixed effects. This will be done using the Matlab function 'fitlme' with REML estimation predicting change from V1 values following each 5 session RS-tDCS interval (Matlab, R2020a, The MathWorks Inc.).

Given that the purpose of this pilot study is to develop effect sizes for a subsequent R01, we will also derive least-squares means effect sizes of our research strategy on distress, NA, percentage of days of use in 4 intervals [V1-V5; V6-V10; V11-V15; V16-V20]. The number of days that elapsed in each interval will be used as a covariate.

CONFIDENTIAL

This material is the property of the NYU School of Medicine and Langone Medical Center. Do not disclose or use except as authorized in writing by the study sponsor
Interventional Template Version: 11 January 2019

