10.4.4 Adherence and Retention Analyses

Compliance with the interventions will be assessed by summarizing the distributions of numbers and proportions of completed sessions by intervention group. Supportive analyses will evaluate the effects of compliance on results for the primary outcome of change in distress from baseline to end of treatment. Compliance measures will be incorporated into the primary outcome of Aim 1 (distress) analysis models to estimate the effect of compliance on the primary outcome.

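### Sections 4.2.1 and 10.2 disagree on which outcomes are primary, and the 10.2 conclusion rule fixes no outcome, level, direction or treatment-end contrast

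*Combined protocol and SAP*

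**What the plan says.** **Primary endpoints (4.2.1).** Distress is measured by K10 and PANAS. Cannabis use is measured by TLFB, MCQ-17 and two further instruments: "and Quantity of Cannabis-Use Inventory (DFAQ-CU) and Cannabis Withdrawal Scale (CWS) between baseline and treatment-end". That makes six instruments, all as change from baseline to treatment-end.

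**Hypotheses (10.2).** The treatment-by-time interaction is tested on (1) distress, by K10 and PANAS-NA, and (2) use, by TLFB, "with additional outcomes addressing mood/anxiety (BDI, STAI), detailed cannabis use (DFAQ-CU), craving (MCQ-17) and withdrawal (CWS". The conclusion rule follows: "If the interaction effect for an outcome is significant, we will conclude there is statistical evidence of overall treatment effect".

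**Analysis (10.4.2).** The section covers primary and secondary endpoints together and labels none of its measures primary. Its model list is "The dependent measures (K10 score, NA, percent of days of use, CWS, MCQ-17"; DFAQ-CU is absent. It also says: "Given that the purpose of this pilot study is to develop effect sizes for a subsequent R01".

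**Direction and timepoint elsewhere.** The Protocol Summary words the endpoint as "Decrease in Cannabis Use by treatment End". Section 2.3 says active stimulation "will reduce distress and cannabis use in patients with MS". Section 10.4.4 refers to "the primary outcome of change in distress from baseline to end of treatment" without naming an instrument.

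**Level and sample.** The only alpha is the one-sided 0.05 in the sample size calculation (10.5). Section 10.3 runs every analysis in an intent-to-treat and a per-protocol sample and calls neither primary. No multiplicity procedure or hierarchy is given.

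**The concern.** MCQ-17, DFAQ-CU and CWS are primary in one current section and additional in another, and nothing says which section governs. The rule that turns a test into a conclusion is looser than the endpoint it serves. The endpoint is a decrease at treatment-end; the rule asks only for a significant interaction on some outcome.

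Two things are at stake. The trial could report a treatment effect under its own rule when the treatment-end change does not support one. And the instrument that carries each aim could be chosen after results are known, most plainly between K10 and PANAS-NA for Aim 1.

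**Working it through.** **1. The lists side by side**

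| Measure | 4.2.1 | 10.2 | 10.4.2 model |
|---|---|---|---|
| K10 | primary | hypothesis 1 | yes |
| PANAS | primary (not limited to negative affect) | hypothesis 1 (negative affect) | yes (negative affect) |
| TLFB | primary | hypothesis 2 | yes (percent of days) |
| MCQ-17 | primary | additional | yes |
| CWS | primary | additional | yes |
| DFAQ-CU | primary | additional | no |

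The conflict in status is between 4.2.1 and 10.2. Section 10.4.2 adds only that DFAQ-CU has no place in the five-visit model.

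**2. What the rule accepts.** With visits as categories, let d be the vector of the four active-minus-sham differences in change from V1 (sessions 5, 10, 15, 20) and V its covariance matrix. The interaction hypothesis is d = 0, and the Wald statistic is Q = d' V⁻¹ d.
- Q(d) = Q(−d), so an effect favouring sham is as significant as the same effect favouring active.
- Q can be large when only the session 5, 10 or 15 component is non-zero, so no treatment-end difference is required.

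Section 10.2 also allows continuous time if plots suggest a trend. A two-sided slope test has no built-in direction either.

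**3. The plan's own sizing.** DE = 1 + (5 − 1) × 0.8 = 4.2, and 50 × 4.2 / 5 = 42, split 28 and 14. This reproduces. The one-sided 0.05 and 80% power belong to this calculation; 10.5 does not link them to the interaction test.

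**4. False-claim rate if more than one measure can carry a claim.** Assumptions not in the documents: one-sided 0.05 per test, no true effect, and equally correlated normal test statistics with correlation r from 0 to 0.9. For k measures:

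rate = 1 − ∫ φ(t) · Φ((1.645 − √r·t) / √(1 − r))^k dt

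At r = 0 this is 1 − 0.95^k: for k = 2, 1 − 0.9025 = 0.0975; for k = 3, 1 − 0.8574 = 0.1426.

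| r | 0 | 0.3 | 0.5 | 0.7 | 0.8 | 0.9 |
|---|---|---|---|---|---|---|
| k = 1 (outcome by outcome) | 5% | 5% | 5% | 5% | 5% | 5% |
| k = 2 (K10 or PANAS-NA for Aim 1) | 9.8% | 9.3% | 8.8% | 8.0% | 7.5% | 6.8% |
| k = 3 (any core measure of 10.2) | 14.3% | 13.0% | 11.8% | 10.3% | 9.3% | 7.9% |

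Zero correlation is unlikely for K10 and PANAS-NA, since both measure distress. The k = 2 row also gives the chance of at least one false conclusion when two aims, with one measure each, are concluded separately.

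**5. Power if Holm were used across the two aims.** From 10.5, the Aim 1 shift is 1.6449 + 0.8416 = 2.4865. For Aim 2, assume power scales from the 15 needed to the 28 planned at the same allocation ratio: 2.4865 × √(28/15) = 3.397.
- Power at one-sided 0.05: Aim 1 0.800; Aim 2 P(Z > 1.645 − 3.397) = 0.960.
- Power at one-sided 0.025: Aim 1 P(Z > 1.960 − 2.4865) = 0.701; Aim 2 0.925.
- Holm at r = 0, Aim 1: 0.701 + (0.800 − 0.701) × 0.925 = 0.79.
- Holm at r = 0, Aim 2: 0.925 + (0.960 − 0.925) × 0.701 = 0.95.

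Simulated up to r = 0.9, Aim 1 stays at about 79% to 80%, and Aim 2 falls from about 95% to 92.5%.

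**The case against.** **Section 10.2 already ranks its outcomes.** It has two numbered hypotheses and a separate group of additional ones, 10.5 sizes the two aims independently, and *overall* most naturally means across time points for one outcome. This stands: on that reading each test keeps its own level. A reader might instead infer that any one of the six instruments suffices for a trial-level claim, with a much larger error rate. The documents do not say that, and it is not the basis of this point.

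**Section 10.4.2 is not a third primary list.** Correct. The absence of DFAQ-CU may simply reflect when it is collected: its row in the Schedule of Events carries fewer marks than MCQ-17 or CWS, although the table is too broken to confirm the visits. The conflict between 4.2.1 and 10.2 does not depend on this.

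**The rule speaks of an effect, not a benefit, and direction is stated elsewhere.** Direction is indeed given in the Protocol Summary and 2.3. But the rule does not refer to either, and any two-sided interaction test ignores it. One might try to quantify how often a significant interaction lacks a treatment-end difference. That depends on how time is modelled, which 10.2 leaves open, and under no true effect those cases already lie inside the 5%. The gap is one of meaning, not extra error.

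**On a two-sided 5% test the inflation nearly vanishes.** If either distress measure suffices, false claims of benefit are only 4.9% to 3.5% (correlation 0 to 0.9). True, but the plan does not fix sidedness, and the only level it gives is one-sided 0.05.

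**It is a pilot for effect sizes.** This lowers the stakes. It does not remove a formal conclusion rule that the plan still contains.

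**Conclusion.** The point holds and should be fixed. Sections 4.2.1 and 10.2 give MCQ-17, DFAQ-CU and CWS different status, and the 10.2 rule can be met by a result that does not support the primary endpoint: one favouring sham, or one confined to an intermediate visit.

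The size depends on the reading. Outcome by outcome there is no inflation. If either K10 or PANAS-NA can carry Aim 1, the false-claim rate is 9.8% to 6.8%. If any of the three core measures suffices, it is about 14.3% to 7.9%. Both ranges rest on the assumed one-sided 0.05 per test and correlation 0 to 0.9. Multiplicity is therefore the smaller part of the problem; the larger part is that the rule is not tied to the endpoint.

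**What to change.** - Use one outcome list in 4.2.1, 10.2 and 10.4.2, with MCQ-17, DFAQ-CU and CWS as supportive outcomes, as 10.2 already treats them.
- Name one measure per aim to carry the conclusion: K10 or PANAS-NA, at the sponsor's choice, for Aim 1; TLFB percent of days of use for Aim 2. Date the choice and fix it before those choosing can see unblinded data. Section 8.1 unblinds each participant at the 3-month follow-up, so this matters before the trial ends.
- Apply the 10.2 rule per aim to the active-minus-sham change from baseline to treatment-end, in the favourable direction, at one-sided 0.05 to match 10.5, in the intent-to-treat sample.
- Report all other measures as estimates with confidence intervals.
- Alternatively, if only effect sizes for the later grant are wanted, delete the conclusion rule. This gives up a formal efficacy conclusion.

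**Cost.** Wording only; no new data. Craving and withdrawal can no longer carry a primary claim. With the aims concluded separately, the chance of at least one false aim-level conclusion is 9.8% to 6.8% (correlation 0 to 0.9) and should be disclosed. A correction across aims is needed only if a single trial-level claim from either aim is intended. Holm would then cost little: on the effects assumed above, power is about 79% for Aim 1 (from 80%) and about 95% to 92.5% for Aim 2 (from 96%).

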10.4 Description of Statistical Methods

10.4.1 General Approach

Prior to formal statistical analysis, summary statistics for all variables will be obtained and graphical displays will be generated (e.g., spaghetti plots, boxplots). All behavioral outcome measures will be based on standardized composite scores from the literature. These analyses will be used to identify potential heterogeneity and imbalance of randomization into the intervention arms within strata.

All baseline characteristics will be evaluated and considered for inclusion as covariates in the supportive and secondary comparative analyses based on baseline differences among treatment groups and clinical importance. We will also use data reduction techniques (such as factor analysis or principle component analysis) to confirm the applicability of the composite scores in our population.

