10.5 Sample Size

Power analyses were conducted independently for Aim 1 and Aim 2, wherein estimated effect sizes came from 2 independent manuscripts that used tDCS to measure changes in distress (Aim1) and estimated changes in cannabis use (Aim 2). In the planned study subjects will be assessed at 5 time points with the Change from V1 being used as a dependent variable (4 pieces of data per dependent measure per participant).

There is an anticipated interclass correlation coefficient (ICC) of 0.8 for the within-subjects measures. The design effect which accounts for multiple correlated observations within each subject, is estimated to be 4.2 ($DE = [1 + (5-1) 0.8]$). In a clustered setting, the sample size is $N_{\text{effective}} = nm/DE$ where n is the number of subjects required when m replications within participants are performed after accounting for the design effect (DE). The estimated number of individuals needed to detect an effect in the active RS-tDCS group is 28 for Aim 1 and 15 for Aim 2 (1-sided alpha of 0.05 and power of 80%).

CONFIDENTIAL

This material is the property of the NYU School of Medicine and Langone Medical Center. Do not disclose or use except as authorized in writing by the study sponsor
Interventional Template Version: 11 January 2019

For this study, we will utilize a 2:1 randomization based on pragmatic considerations including timeline, cost, and the added value of over recruiting to the Active group in order to have a better assessment of safety and tolerability data. In corporation this information into the total planned recruitment size, we arrived at n=42(=50 * 4.2 / 5). (28 allocated to active, 14 allocated to sham). We anticipate enrolling 52 participants which includes 10% drop out rate.

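### Section 10.2 lets outcome plots choose the time coding of the treatment-by-time test, with no selection rule; a nominal 5% test could then run at anything from about 5% to about 12% per outcome

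*Combined protocol and SAP*

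**What the plan says.** Section 10.2 sets the test and the decision rule together. The hypotheses concern a treatment-by-time interaction on distress (K10, PANAS-NA) and use (TLFB), with further outcomes for mood, anxiety, detailed use, craving and withdrawal. The rule is applied outcome by outcome: "If the interaction effect for an outcome is significant, we will conclude there is statistical evidence of overall treatment effect". The next sentence opens the form of that term: "If the spaghetti plots suggest trends (e.g., linear, quadratic, or piecewise changes) we will treat time as a continuous variable". In that case the analysts will "fit repeated measures regression models along with group and its interaction with continuous time as independent variables".

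Section 10.4.1 gives the timing: "Prior to formal statistical analysis, summary statistics for all variables will be obtained and graphical displays will be generated (e.g., spaghetti plots, boxplots"). It adds that this preliminary work serves to "identify potential heterogeneity and imbalance of randomization into the intervention arms within strata". It does not say whether the spaghetti plots are drawn by arm or pooled.

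Section 10.4.2 names linear mixed models fitted by REML to change from V1. The dependent measures "will be nested within timepoint (Visit 1, 5, 10, 15, 20), with active/sham as fixed effects". The assessments are therefore discrete, but the section does not say whether time enters as a factor or as a number, and it does not mention the interaction.

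The only significance level is in section 10.5, for the sample size: "1-sided alpha of 0.05 and power of 80"%. Section 10.2 states neither a level nor a direction for the interaction test.

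**The concern.** A p-value has its stated meaning only if the form of the test does not depend on the feature of the data being tested. Here the feature is how the two arms diverge over time. If the analyst sees that divergence and then picks the shape that describes it best, the test is tuned to the noise in this sample, and false positives exceed the nominal rate. The choice is open separately for each outcome, including K10, PANAS-NA and TLFB, which carry the two primary objectives. At stake is whether a significant interaction can be read at its stated level.

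This is more than missing detail. The plan contains an explicit provision that makes the model depend on the plots, and nothing elsewhere limits how that provision is used.

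**Working it through.** **The plan's own sample size.** The design effect is 1 + (5 − 1) × 0.8 = 4.2. The total is 50 × 4.2 / 5 = 42, split 2:1 into 28 active and 14 sham. This reproduces section 10.5, and these figures feed the check.

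**Inputs.**
- Arms of 28 and 14 (section 10.5). A run with 35 and 17, roughly the 52 enrolled, was added.
- Five assessments (section 10.4.2).
- Correlation: "There is an anticipated interclass correlation coefficient (ICC) of 0.8 for the within-subjects measures" (section 10.5), taken as equal between all pairs of visits.
- Assumed, because the plan does not say: a 5% level for the F test, normal errors and complete data.

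**Test for each coding.** With N = 42 participants and T = 5 visits, and d degrees of freedom for the group-by-time term,

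F = (SS for group-by-time / d) ÷ (residual SS / (N(T − 1) − 2d)).

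N(T − 1) = 168, so the denominator degrees of freedom are 160 for categorical time (d = 4), 166 for linear (d = 1) and 164 for quadratic or one-knot piecewise (d = 2).

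**Three ways the plots might be used.**
1. Pooled: choose the coding by AIC on the overall time trend, blind to arm.
2. Arms visible: choose by AIC with the group-by-time term in the model.
3. Most favourable: report the coding with the smallest p.

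**Results.** Null false-positive rates, 28:14, no common trend, 20,000 simulated trials per setting. The Monte Carlo standard error is about 0.15 to 0.23 percentage points.

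| Codings available | Pooled, arm-blind | By fit, arms visible | Smallest p |
|---|---|---|---|
| Categorical, linear | 4.8% | 7.1% | 8.1% |
| + quadratic | 4.9% | 8.3% | 9.4% |
| + piecewise, one knot | 4.8% | 8.8% | 9.9% |
| + piecewise, three candidate knots | 4.8% | 10.2% | 11.5% |

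Each coding used alone and fixed in advance gives 4.7% to 4.8% in this setting.

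**Sensitivity.** The other settings were 35:17, a common linear trend and a common plateau. Over all settings, a fixed coding gives 4.5-5.3%, the pooled choice 4.8-5.2% and the smallest p 7.8-12.2%. The arms-visible choice spans 6.0-10.8%. Its low end, 6.0-8.1%, comes from the common plateau, where the shared curve partly settles the shape.

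**On the plan's four change scores.** Sections 10.4.2 and 10.5 analyse change from V1, so there are four values per participant. Taking V1 away from every later value does not alter a participant's pattern across the four later visits, so the same calculation applies with T = 4 and a categorical term with d = 3. The smallest p gives 8.2% (categorical, linear), 9.3% (+ quadratic), 10.0% (+ one knot) and 10.5% (+ both possible knots). The arms-visible choice gives 7.7% to 9.8%, the pooled choice 5.1% to 5.2%, and a fixed coding 4.9% to 5.0%.

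**The case against.** A reader might infer that the plan's test runs at 9-12%. The documents do not support that. They mention no AIC, no search for the smallest p and no search over knots. The upper figures describe what the wording permits, and with a pooled, arm-blind look there is no inflation.

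Two further inferences go beyond the text. The first is that the arms are visible when the shape is chosen. The purpose stated in section 10.4.1 is a check of heterogeneity and randomization balance. That needs arm labels in some summaries, but it does not establish that outcome trajectories are plotted by arm. The second is that the plot-chosen test decides efficacy. The conclusion rule stands before the plot sentence, and the text does not say whether the continuous-time model replaces the first test or only describes its shape. The decisive reading is natural, because the sentences are adjacent and only the models in the next paragraph are called supplementary, but it remains a reading.

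Section 10.4.2 also points towards discrete assessments, and it describes the trial as a pilot meant to supply effect sizes for a later grant application.

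These points limit the size and the severity. They do not remove the problem: section 10.4.2 does not lock the coding, no passage requires arm-blind plots, and section 10.2 commits to a conclusion of treatment effect whatever the trial is called.

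**Conclusion.** The point stands as an open choice in a deciding test, and it should be fixed. On an assumed 5% level, the false-positive rate per outcome can lie at about 5% (pooled, arm-blind choice), about 7-11% (choice by fit with arms visible, or lower if both arms share a strong curve) or about 8-12% (most favourable coding reported; about 8-10% on four change scores). The documents do not say which applies, so no single figure can be attributed to the plan.

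The figures rest on equal correlation of 0.8, normal errors and complete data. The 5% level is borrowed from section 10.5, where it is one-sided. A multi-degree-of-freedom interaction test has no direction, so the level and sidedness of the real test also need to be stated.

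**What to change.** In section 10.2, state that one pre-specified coding decides for every outcome, whatever the plots show. A natural choice is time as a factor at the scheduled assessments, which agrees with the discrete visits in section 10.4.2. State the within-participant covariance and the significance level in the same place. Label linear, quadratic and piecewise models as sensitivity analyses that cannot change the conclusion.

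Two alternatives also hold the level: pre-specify a linear contrast as the deciding test, or choose the shape only from pooled data without arm labels, under a rule written beforehand.

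The cost is about two sentences, with no added participants, visits or data. A fixed categorical test has somewhat less power against a truly linear divergence. If the covariance is left unstructured, five visits need 5 × 6 / 2 = 15 parameters, which is many for 42 participants. A simpler structure can be named instead, provided it is named in advance.
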